Aim 1: In persons with TBI, prospectively compare overnight sleep efficiency in a cohort exposed to morning Bright White Light with a comparison group exposed to Red Light in an acute inpatient rehabilitation setting.

Aim 2: Explore the relationship between Bright White Light exposure during inpatient rehabilitation after TBI and mood, therapy participation, attention, rate of functional recovery and length of stay.

Aim 3: Develop and describe sleep study procedures on the inpatient rehabilitation unit for persons with TBI to support optimal and feasible design of future studies in this important area.

Research Hypothesis:

In persons with TBI, prospectively compare overnight sleep in a cohort exposed to morning Bright White Light with a comparison group exposed to Red Light in an acute inpatient rehabilitation setting.

Hypothesis 1: Individuals exposed to Bright White Light for 30 minutes each morning will have better sleep compared to the Red Light exposure group, as measured by sleep efficiency.

Hypothesis 2: Individuals with daily morning Bright White Light exposure will have better mood (as measured by the Positive and Negative Affective Schedule, PANAS), therapy participation (as measured by a 0-100 therapist rating) and attention (as measured by the Symbol Digit Modalities Test) at 10 days compared to individuals with daily Red Light exposure. The group exposed to Bright White Light will also have less daytime sleepiness and fatigue (as measured by the Karolinska Sleepiness Scale (KSS) and the Barrow Neurological Institute Fatigue Scale (BNI-FS), a faster rate of functional recovery as measured by FIM™ efficiency for the rehabilitation stay and a shorter length of stay compared to those in the Red Light group

Hypothesis 3a: Bright White Light exposure will be rated as a reasonable addition to clinical care by staff using Likert scale ratings. Categorize and quantify rates of any side effects of Bright White Light and Red Light exposure in persons with TBI during inpatient rehabilitation.

Hypothesis 3b: Bright White Light and Red Light exposure will be generally well tolerated with side effect profiles and rates similar to those observed in previous studies with other populations.

[figure not shown]
See Appendix for Flowchart on Specific Aims of this study

V. Study Description

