The screening process will begin will reviewing the medical charts for patients that are on the inpatient rehabilitation unit at Harborview Medical Center. If a patient meets the inclusion criteria, research staff will approach the patient to determine whether the patient is cognitively capable of giving their consent for the study by administering the Galveston Orientation and Amnesia Test. The study will then be explained to the patient; or if the patient is experiencing post traumatic amnesia, the study will be explained to the patient’s legally authorized representative. Consent will be obtained either from the patient or, if he or she is unable to provide informed consent, the patient’s legally authorized representative.

VII. Study Sample:

Study participants will be recruited from acute inpatient rehabilitation at three participating TBI Model Systems institutions (University of Washington, Mount Sinai, Baylor). Eligible participants will be within three months of sustaining a moderate to severe TBI (as defined by the TBI Model Systems (Traumatic Brain Injury Model Systems, 2013)), admitted to acute inpatient rehabilitation, English speaking, and aged 18-70 years. Exclusionary medical factors will be identified in the medical record and through interview during screening/baseline assessment. In a pilot study comparing the effects of BWL and RL exposure in a sample of subjects with chronic TBI, Cantor et al. (Cantor, et al., 2012) reported an effect size of 0.63 for sleep duration. Because this pilot study involved subjects in the chronic phase of TBI, who were living at home rather than in an institution, and underwent a longer course of treatment (28 days in that study vs. 10 days in this study), we chose to take a conservative approach to calculating the required sample size. Based on an estimated effect size of 0.5 and 80% power, 128 subjects would be required to complete this study (64 per group). We anticipate recruitment over three years at three sites. Historical TBIMS and associated trial enrollment totals from the participating sites supports this study enrollment goal.

VIII. Inclusion Criteria:

1. Within three months of moderate to severe TBI
2. Admitted to acute inpatient rehabilitation
3. Ages 18-70
4. English speaking

VIII. Exclusion Criteria:

1. Complete blindness
2. Absence of eye opening or disorders of consciousness (Rancho level of 1-3)
3. Past medical history of retinal pathology
4. Past medical history of light sensitivity

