- [42] **Functional Independence Measure (FIM)** is the most widely accepted functional assessment measure in use in the rehabilitation community. The FIM™ is an 18-item ordinal scale, used with all diagnoses within a rehabilitation population. It is viewed as most practical for assessment of progress during inpatient rehabilitation (State University of New York at Buffalo, 1997) and is assessed as part of normal rehabilitation care at admission and discharge from the rehabilitation unit. FIM™ efficiency is simply the change in FIM™ score divided by the length of rehabilitation stay and is used as marker of relative speed of functional change. We will evaluate for effects on both FIM™ motor and FIM™ cognitive scores.
- **Symbol Digit Modalities Test[43]:** The SDMT is a pencil and paper test for attention that takes approximately five minutes to administer and is frequently used in evaluations after TBI (DeMonte,

2009)) (Kalmar K, 2008) (Hanks R, 2008). The SDMT will be administered at enrollment and after intervention. The Interagency Workgroup on TBI Outcomes selected the Symbol Digit Modalities Test as CORE common data elements in TBI outcomes research.

- Positive and Negative Affect Schedule: The 20-item Positive and Negative Affect Schedule (PANAS), developed with a sample of undergraduate students and validated with adult populations, comprises two mood scales, one measuring positive affect and the other measuring negative affect. Each item is rated on a 5-point scale ranging from 1 = very slightly or not at all to 5 = extremely to indicate the extent to which the respondent has felt this way in the indicated time frame. This scale is used to measure affect over a range of times including: at this moment, today, the past few days, the past week, the past few weeks, the past year, and generally (on average). Watson et al. (Watson, 1988) reported Cronbach's alpha coefficients for the various time reference periods ranging from .86 to .90 for the Positive Affect scale and .84 to .87 for the Negative Affect scale. For the general period, alpha was .88 for Positive Affect and .87 for Negative Affect. Test-retest correlations for an 8-week period ranged from .47 to .68 for Positive Affect, .39 to .71 for Negative Affect (for the general time period, Positive Affect stability = .68, Negative Affect Stability = .71[44]).

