- 3) Clinical Staff feedback: phototherapy intervention will rated using a likert scale on the following categories:

- a. Ease of use
- b. Perceived relevance to rehabilitation care
- c. Impression of effectiveness.

Post Light Therapy Outcome Assessment

Day 13: At the conclusion of the light therapy sessions (and prior to discharge from rehabilitation), a blinded Outcomes Examiner will complete the post therapy outcome assessment. This assessment will include the following:

- Symbol Digit Modalities Test
- Positive and Negative Affect Schedule (PANAS)
- Barrow Neurological Fatigue Scale

XII. Data Analysis

The primary outcome is the between-group difference (BWL vs. RL exposure) in average sleep efficiency at baseline compared to after 10 days of light treatment. ANOVA will be used to compare groups controlling for demographics, injury severity, and use of medications.

Secondary outcomes (mood, therapy participation, attention, daytime sleepiness/fatigue) between groups assessed at baseline and after 10 days of light therapy will be compared using repeated measures ANOVA. FIMTM efficiency and inpatient rehabilitation length of stay will also be compared between groups using ANOVA controlling for the same variables as the primary outcome. Descriptive analysis will summarize responses to the nursing burden questions including estimated staff time for the intervention.

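### The length-of-stay and FIM-efficiency models leave out admission FIM, which the trial already collects; this probably costs precision for length of stay and may cost little for FIM efficiency

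*Combined protocol and SAP*

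**What the plan says.** Section XII (Data Analysis) sets the covariates for the primary sleep outcome: "ANOVA will be used to compare groups controlling for demographics, injury severity, and use of medications". It then says that FIM efficiency and inpatient rehabilitation length of stay "will also be compared between groups using ANOVA controlling for the same variables as the primary outcome". No functional score is named for either model. The remaining secondary outcomes (mood, participation, attention, sleepiness and fatigue) go into repeated measures ANOVA together with their baseline values.

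Both outcomes belong to Hypothesis 2 in Section IV, which predicts "a faster rate of functional recovery as measured by FIM™ efficiency for the rehabilitation stay and a shorter length of stay" in the bright-light arm. Aim 2, which covers them, is worded as exploratory.

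Section X.D says that the FIM "is assessed as part of normal rehabilitation care at admission and discharge from the rehabilitation unit". It defines FIM efficiency as the change in FIM over the stay divided by the length of the stay, and it plans to look at motor and cognitive scores. Table 1 gives FIM its own row as a functional score, marked in the Day 0-2 column and at outcome. The injury-characteristics row is separate and holds cause, date, GCS and PTA. Under Section XI, randomization follows baseline testing on Day 2 and is stratified by center and sleep-disturbance severity only.

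**The concern.** A patient's functional level on entering rehabilitation is a plausible predictor of how long the stay lasts. The trial holds that measurement at no extra cost but does not use it in the model for length of stay. None of the three listed covariate groups measures function on admission. Section VIII lets patients enter up to three months after injury, so an emergency-department GCS may say little about function at rehabilitation admission.

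What is at stake is the width of the confidence interval for the difference in length of stay, and possibly for the difference in FIM efficiency. Randomization is not stratified on function, so the arms can differ on it by chance. Adjustment would remove the part of that noise that admission FIM explains. Prespecification matters too, because a covariate added after the data are seen is open to the charge of selective choice.

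**Working it through.** **Inputs from the plan.** Section VII sizes the trial "Based on an estimated effect size of 0.5 and 80% power", giving 128 completers, 64 per group. The 0.5 was lowered from a pilot that "reported an effect size of 0.63 for sleep duration", so it belongs to sleep and not to length of stay or FIM. Allocation is 1:1 (Section XI). Alpha is not stated.

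**Assumptions.** Two-sided alpha of 0.05. A true effect *d* of 0.5 or 0.3, in units of the residual SD after the covariates already planned. A partial correlation *r* between admission FIM and the outcome, given those covariates, of 0 to 0.7. The documents give no SD, effect size or correlation for either outcome.

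**Step 1: reproduce the plan's figure.** The normal approximation gives n per arm = 2(1.96 + 0.842)² / 0.5² = 62.8, so 63 per arm. With the noncentral t, power is 79.5% at 63 per arm and 80.1% at 64. The stated 64 per group reproduces. A one-sided 0.05 would give 50, so two-sided 0.05 is the reading that fits.

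**Step 2: add admission FIM.** The residual SD is multiplied by √(1 − r²), so the noncentrality is [d / √(1 − r²)] × √(n/2), with n = 64 and one degree of freedom fewer (125 instead of 126). For d = 0.5:

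- r = 0: 0.5 × √32 = 2.83, power 80.1%.
- r = 0.5: √0.75 = 0.866, and 2.83 / 0.866 = 3.27, power 90.0%.

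| Partial r | Cut in SE | Power, d = 0.5 | Power, d = 0.3 |
|---|---|---|---|
| 0 | 0% | 80.1% | 39.1% |
| 0.1 | 0.5% | 80.5% | 39.5% |
| 0.2 | 2.0% | 81.7% | 40.5% |
| 0.3 | 4.6% | 83.7% | 42.3% |
| 0.5 | 13.4% | 90.0% | 49.4% |
| 0.7 | 28.6% | 97.6% | 65.5% |

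The r = 0 row is the model without admission FIM.

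**Step 3: chance imbalance.** The standardized difference between arms in admission FIM has standard error √(2/64) = 0.18, so a 95% range of about ±0.35 SD. At an assumed r of 0.5, an imbalance at that limit shifts the unadjusted contrast by 0.5 × 0.35, about 0.17 SD. This is the same variance that Step 2 removes, seen in a single trial. It is not an additional loss.

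**Step 4: do the two outcomes behave alike?** An illustrative simulation took admission FIM with mean 55 and SD 18, a median stay of 22 days, and discharge FIM with mean 92 and varying dependence on admission FIM. All of these are assumed values. The correlation of admission FIM with length of stay was −0.28 to −0.65. With FIM efficiency it ran from −0.23 to +0.51 and passed through zero. Patients admitted with low scores have more to gain, while patients admitted with high scores have shorter stays, and the two effects pull the ratio in opposite directions. At |r| of 0.1 or less, leaving the covariate out costs under half a point of power at d = 0.5.

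**The case against.** A reader might infer that both Hypothesis 2 tests lose power. The documents do not support that. Admission FIM is already subtracted inside FIM efficiency, which is a rate over the whole stay and has no baseline value of its own. Its remaining correlation with admission FIM could be near zero or of either sign. This objection stands, and the point is firm only for length of stay.

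A reader might also take the rise from 80% to 90% as a property of these tests. It is not. The 0.5 is borrowed from sleep, no power is claimed for either outcome, and the partial correlation is assumed. PTA is among the injury data, and some patients are still in PTA at enrollment. If PTA is the severity measure used (Section XII does not say), it may absorb part of what admission FIM would explain, so the relevant r is likely to be smaller than the raw correlation. That stands as well, which is why the table starts at zero.

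Chance imbalance is not bias. Under randomization the standard error already allows for it. The argument that patients admitted near the FIM ceiling can gain little is not developed here, because the documents give no admission FIM distribution and one linear covariate would not remove a ceiling.

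Finally, the FIM form in the Appendix lets items be coded as unknown or assessed after 72 hours, so adding the score without a rule could drop patients. This is a fair objection to a bare fix, and a simple rule meets it.

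These objections reduce the size and weight of the point. They do not remove the omission, and none of them is a reason to leave the covariate out.

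**Conclusion.** The concern holds in a limited form. Section XII omits a baseline score that the trial already has. Whatever variance in length of stay that score explains beyond demographics, injury severity and medication use is left in the error term. For FIM efficiency the loss may be negligible.

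At an assumed 0.5 SD effect, the gain from adding the score is 0.4 points of power at partial r = 0.1, 3.6 at 0.3 and 9.9 at 0.5. At an assumed 0.3 SD effect and r = 0.5, it is 10.3 points (39.1% to 49.4%). These figures rest on assumed effects and correlations, two-sided 0.05 and 64 completers per arm.

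This is a matter of precision in secondary outcomes. It does not bias the comparison, and it touches neither the primary sleep analysis nor the 128.

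**What to change.** In Section XII, add to the listed covariates:

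- total admission FIM in the length-of-stay model;
- admission FIM motor score in the FIM motor efficiency model, and admission FIM cognitive score in the FIM cognitive efficiency model.

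State a rule for admission scores coded unknown: a simple imputation from baseline data only, or a missing indicator, so that no patient is dropped because of the covariate. The rule matters mainly for length of stay. In the efficiency models, a missing admission score leaves the outcome itself undefined.

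The cost is a sentence or two of analysis text and one or two degrees of freedom per model (one for the score, one more if an indicator is used). No new data are needed and no burden falls on patients. If admission FIM turns out to explain nothing, those degrees of freedom are all that is lost.

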We propose to recruit a prospective cohort of persons with TBI to compare effects of Bright White Light exposure to Red Light (RL) exposure. Light therapy treatments will be given daily in the morning for up to 10 days, and an Actiwatch will be worn that records movements for the entirety of the study. We will utilize objective assessments of sleep quality, subjective mood report, rate sleepiness and fatigue and complete measures of attention and participation in rehabilitation therapies to explore the

effects of light exposure in the acute inpatient rehabilitation setting. We will also evaluate the anticipated device costs and staff burden involved in utilizing light therapy exposure in the inpatient rehabilitation clinical setting. An overview of study procedures with timeline is described in Figure 1 below with further details in the sections that follow.

Figure 1. Overview of Study Procedures for TWILIGHT

VI. Screening for Eligibility:

Although subjects will be screened for this study concurrent with screening for eligibility for enrollment into the Traumatic Brain Injury Model System (TBIMS) study (Traumatic Brain Injury Model Systems, 2013), these are independent studies and subjects will have the choice to enroll in both, neither, or either one. The TBI Model Systems program, sponsored by the National Institute on Disability and Rehabilitation Research (NIDRR), is the largest longitudinal study of TBI in the nation. NIDRR awards 5 year grant awards to institutions that are national leaders in medical research and patient care and these. Institutions which receive this distinction are collectively termed, the TBI Model Systems. As part of the TBI Model Systems, the University of Washington TBI Model Systems research team is recognized as providing the highest level of comprehensive specialty services from the point of injury through chronic care stages, including re-entry into full community life. The current grant cycle is for the 2012-2017 time period, and one of the areas of interest for the UW TBI Model Systems research team is the treatment of sleep difficulties after TBI.

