- Therapy Participation: Participation in rehabilitation therapies will be evaluated at enrollment and again after light therapy (day 13) by the subject's therapist using a 0-100 scale of cooperation with therapy that has been previously utilized in this population.[45]
- Karolinska Sleepiness Scale (KSS): The KSS is a well-validated, widely used single question survey that examines current sleepiness.
- Barrow Neurological Institute Fatigue Scale (BNI-FS): The BNI-FS is a scale that was designed to examine fatigue during acute recovery from TBI. It has good internal consistency and appears to specifically examine a single psychometric construct of fatigue in patients with TBI (Wäljas M, 2012).
- Clinician Feasibility Survey: This is a likert scale survey to assess phototherapy intervention for ease of use, perceived relevance to rehabilitation care, and impression of effectiveness. This survey will be available in paper and electronic versions.

XI. Study Procedures:

Screening and Enrollment:

Patients' medical records will be screened for inclusion/exclusion criteria. Informed consent will be obtained from the subjects after they have been determined to be cognitively capable to consent for the study. A subject will be considered unable to give independent consent if they are still in PTA (as measured by the Galveston Orientation & Amnesia Test (GOAT), with a score <76) or their medical record at the time of enrollment specifies that they are unable for other reasons to independently consent. If a subject is unable to consider consent independently, proxy consent will be obtained from the legally authorized representative (LAR). This process is part of obtaining informed consent for the TBI Model System study. In addition, clinical staff and research staff have established communication lines to approach patients at appropriate times that do not interfere with patient clinical care.

Baseline and Randomization:

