- 5. How difficult is it for me to stay alert during activities? _____
- 6. How difficult is it for me to build my energy level once I wake up in the morning? _____
- 7. How difficult is it for me to stay out of my bed during the day? _____
- 8. How difficult is it for me to stay alert when I am not involved in something? _____
- 9. How difficult is it for me to attend to something without becoming sleepy? _____
- 10. How difficult is it for me to last the day without taking a nap? _____

11. Please circle your **OVERALL** level of fatigue since your injury:

0	1	2	3	4	5	6	7	8	9	10
No problem										Severe Problem

Quarterly Staff Survey

If you have been involved in the care of a patient enrolled in the TWILIGHT Study in the past three months please answer the questions below.

Date: _____

Please check one:

- Rehabilitation Nurse
- Rehabilitation Therapist (PT, OT, SLP, TR)
- Other

Please indicate whether you agree or disagree with the following statements:

Q1: It was easy to integrate light therapy into patient care.

1	2	3	4	5
Strongly Disagree	Disagree	Neither agree or disagree	Agree	Strongly Agree

Q2: Light therapy did not increase my work load.

1	2	3	4	5
Strongly Disagree	Disagree	Neither agree or disagree	Agree	Strongly Agree

Q3: Light therapy should be offered as a routine treatment option in in-patient rehabilitation.

1	2	3	4	5
Strongly Disagree	Disagree	Neither agree or disagree	Agree	Strongly Agree

Comments?

Overview for Study Participants

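### The appended staff survey lacks the planned effectiveness and staff-time items, and its routine-use rating cannot be attributed to Bright White Light as Hypothesis 3a requires

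*Combined protocol and SAP*

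**What the plan says.** The feasibility part of the plan is spread over several places.

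- **Hypothesis (section IV).** Hypothesis 3a concerns one arm only: "Bright White Light exposure will be rated as a reasonable addition to clinical care by staff using Likert scale ratings".
- **Objective (section V).** "We will also evaluate the anticipated device costs and staff burden involved in utilizing light therapy exposure in the inpatient rehabilitation clinical setting".
- **Instrument (section X.D, last entry).** "This is a likert scale survey to assess phototherapy intervention for ease of use, perceived relevance to rehabilitation care, and impression of effectiveness". Section XI, under Clinical Staff feedback, repeats the same three categories.
- **Analysis (section XII).** "Descriptive analysis will summarize responses to the nursing burden questions including estimated staff time for the intervention".
- **Form (Appendix).** The appendix contents list gives Quarterly Staff Survey and Clinician Feasibility Survey as two names for one form. The form asks for a date and staff role, then has three 5-point agreement items and a comment line. It opens with "If you have been involved in the care of a patient enrolled in the TWILIGHT Study in the past three months". Q1 is on ease of integration. Q2 reads "Light therapy did not increase my work load". Q3 asks whether light therapy should be a routine option.

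**The concern.** Two things that the text promises do not appear on the form: a rating of effectiveness and an estimate of staff time. The form also has no field for a patient, a study number or a light type. Hypothesis 3a is about white light, whereas patients are allocated 50:50 to white or red. One answer may therefore draw on experience with both lights, and nothing on the form would let an analyst separate them afterwards.

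These results belong to Aim 3, which is meant to inform the design of later studies, and section I gives low staff burden as a reason for interest in the treatment. Staff time and patient linkage that are not recorded during the trial cannot be recovered reliably once it has ended.

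**Working it through.** The plan states no figure on this point, so the check sets the planned content against the appended form.

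| Planned content | Where promised | Item on the appended form |
|---|---|---|
| Ease of use | X.D, XI | Q1 |
| Perceived relevance | X.D, XI | Q3 (nearest match) |
| Impression of effectiveness | X.D, XI | none |
| Nursing burden | V, XII | Q2, an agreement rating |
| Estimated staff time | XII | none |
| Rating specific to Bright White Light | IV, Hypothesis 3a | none; items refer to light therapy in general |

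**Step 1: survey categories.** Two of the three planned categories have an item and one does not (3 − 2 = 1, effectiveness).

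**Step 2: burden analysis.** Q2 supplies a burden rating. It gives agreement that work load did not rise, not an amount of time, so the staff-time component of the section XII summary has no item.

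**Step 3: other possible sources.** Table 1 has no staff-time and no perceived-effectiveness measure. Its Light Therapy Time row is the patient's exposure. The device log in section XI records when the lamp is switched on and off, which is again exposure. The comment line might attract remarks on either subject, but not systematically.

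**Step 4: attribution to white light.** Section XI describes the same delivery in both arms: a Litebook in a visually identical case, at 12 to 24 inches, for 30 minutes, over 10 morning sessions. Ratings of ease and work load given after red-light patients therefore still say something about delivering white light. That argument does not extend to Q3, or to a future effectiveness item, because an opinion on whether the therapy is worth offering may depend on which light the respondent saw.

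**Step 5: how often answers would mix lights (illustration only).** The documents do not say how many enrolled patients a respondent sees in three months. Assume k patients, each allocated independently 50:50. The chance that the respondent saw both lights is 1 − 2 × 0.5^k:

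- k = 1: 1 − 2 × 0.5 = 0
- k = 2: 1 − 2 × 0.25 = 0.50
- k = 3: 1 − 2 × 0.125 = 0.75

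Under this assumption, the share of respondents who saw a single light falls from 100% to 50% to 25%. Even with good records, some answers will stay unattributable.

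**The case against.** Several arguments on the other side have force.

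- **The burden analysis is not empty.** A reader might infer that the survey cannot deliver any of it. The documents do not support that: Q2 is a burden question, Q1 is close to one, and section XII plans description only. The gap is the staff-time component.
- **Absence from the appendix is limited evidence.** Section XII does not say that its nursing burden questions are those of this survey. The appendix contents list also omits the Symbol Digit Modalities Test, the therapy-participation rating and the medication data sheet that Table 1 cites, and Table 2 refers to a separate Manual of Procedures. A form that is not appended cannot be ruled out, so the claim that staff time will go uncollected is too strong. What can be said is that no described measure collects it.
- **Half of the ratings need not concern red light.** The 50:50 ratio allocates patients. The survey unit is a staff member in a quarter, and Q3 asks for a general opinion. The ratio cannot be carried over to responses.
- **Hypothesis 3a has no comparison or threshold.** Reading it as a formal test that fails imposes something that the plan does not propose. Q3 does fit its idea of a reasonable addition to care, but for light therapy in general.
- **Asking staff which light was used has a cost.** The form is addressed to nurses and therapists. Nurses complete the Makley scale and the physical therapist rates participation, both study outcomes. The documents describe only the Outcomes Examiner as blinded, but the identical cases suggest that drawing raters' attention to allocation is unwelcome.

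The first four points limit the finding and the fifth shapes the remedy. None supplies the missing items or the missing link to arm.

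**Conclusion.** The concern holds in a limited form. The appended survey omits one of the three rating categories set out in sections X.D and XI, and it omits the staff time named in section XII. No other measure described in the protocol fills either gap. The Q3 rating cannot be attributed to Bright White Light, so Hypothesis 3a cannot be answered as worded. Ease and work-load ratings are less affected, and a limited work-load summary remains available.

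This rests on two assumptions: that the appended form is the one in use, as the appendix list indicates, and that no unlisted form collects the missing quantities. The consequence is confined to descriptive feasibility results under Aim 3. The primary outcome, the sample size and the efficacy analyses do not depend on it. It is worth correcting because the change is small and the information is hard to recover later.

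**What to change.** 1. Add one item asking for estimated staff minutes per session and one 1-5 item on impression of effectiveness. If another form already collects these, cite and append it instead. The effectiveness rating is already part of the plan, so the item brings the form into line with the text.
2. Do not ask respondents for the light colour. Have research staff record on the form the study number or numbers of the patients for whom the respondent cared, and link these to arm at analysis.
3. In section XII, state that the relevance and effectiveness ratings will be summarised by light for respondents who saw only one light, with the number who saw both reported alongside. Ease, work load and staff minutes can be summarised over all respondents.
4. If the linkage is not adopted, report the Hypothesis 3a result as applying to light therapy in general.

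The cost is two more questions on a short form, in both its paper and electronic versions, and a small record-keeping task for research staff. Responses that cover both lights will remain unattributable.
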